1. We will utilize multi-parametric anatomical and molecular imaging of LNs, which incorporate measures of anatomy and chemical environment, to evaluate abilities to discriminate metastatic from benign LNs noninvasively *in vivo*. These approaches have already been applied in other applications of malignancy⁵⁻⁷, and we have developed innovative high spatial resolution variants to enable sub-millimeter LN characterization *in vivo*¹. If successful, findings would have relevance for noninvasively mapping the topography of LN malignancy, which could initiate future investigations to ultimately inform surgery decisions and reduce unnecessary LN removal.

2. We will extend our current trial to evaluate sub-clinical internal and external risk factors of secondary lymphedema progression in the arm and upper torso following cancer therapies post-LN removal and test more refined hypotheses regarding how impaired lymphatic pumping, superficial axillary water accumulation, and interstitial adipose accumulation portend secondary lymphedema onset and progression. This work will be significant for understanding prognostic potential of the new internal markers relative to existing risk factors, and it will reinforce using these measures to triage patients for disease-modifying therapies or as endpoints in therapeutic trials.

3. Emerging therapies that utilize CDT with refined approaches in the individual components (i.e. incorporating graded negative pressure) are being utilized in specialized lymphedema outpatient clinics including Vanderbilt Lymphedema Clinic, but formal efficacy trials have not been performed. We will perform a multiple-measures cross-over trial to evaluate the impact of CDT with vs. without graded negative pressure on reducing lymph stasis and internal markers of fibrosis in chronic BCRL states, along with a subgroup of 1 time treatment before and after MRI and nonMRI measures for immediate treatment impact investigation. Improved lymphatic flow has demonstrated the ability to induce lymphangiogenesis in pre-clinical studies⁸, and it will be crucial to demonstrate internal improvements in vivo, relative to basic symptomatology changes which can be subjective and difficult to quantify, to underscore the need for expanding healthcare coverage of these disease-modifying therapies.

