approximately 90minutes. Patients undergoing 2-year monitoring will also undergo these non-MRI measurements at baseline, and every 5-7 months (targeting at 6months) up to 5 total visits within 2 years; and for this same group an MRI will be done at Visit 1 and then as needed based on symptoms, clinical therapies provided increasing risk of lymphedema such as radiation, and non-MRI measures at subsequent follow-up visits within the 2 year time period. For these follow-up visits non-involving MRI, the visits last approximately 30 minutes.

Perometer

L-Dex

LymphaTouch

MoistureMeter D/LymphaScanner

InBODY 770 (Body Composition)

SkinFibroMeter

5. For subjects enrolled in Aim 3 of this study, they will receive the above mentioned non-MRI and MRI measures (#2) at Visits 1, 11, 12 and 22. In addition the MLD screening form will be completed on Visit 1 in preparation for this component of their CDT during subsequent treatment visits, as well as completion of the Functional Outcome Measures (PSFS and UEFI) patient self-reports will be done on Visits 1, 11, 12 and 22 to establish baseline functional level and monitor during treatments. Then they will receive their assigned therapy intervention (CDT alone or CDT with graded negative pressure) at Visits 2-10 and 13-21. For Group 1, the first course of treatment will be CDT alone, then the second course of treatment will be CDT with graded negative pressure. For Group 2, the first course of treatment will be CDT alone, then the second course of treatment will be CDT with graded negative pressure. During all courses of treatment, it will consist of 9 visits within 6-8 weeks at 75minutes duration each visit, twice per week for three weeks and then once per week for 3-5 weeks. There will be a 4-8 week washout period between Visit 11 and Visit 12.
6. For the subgroup of subjects enrolled in the 1 time hourly treatment visit of Aim 3, they will receive the above mentioned MRI and nonMRI measures before and immediately following the 1x hourly treatment. The PSFS and UEFI questionnaires will not be administered for this 1x treatment visit only. The participants will undergo (i.) CDT alone, (ii.) CDT with graded negative pressure, or (iii.) exercise and self management treatment. This subgroup participation may involve undergoing all three of the single treatment options on different study dates if the participant is interested otherwise the study only only involves this one-time study visit.

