8.0 Statistical analysis plan

Statistical analysis will be overseen by statistician co-investigators. Means, standard deviations, and ranges for continuous variables will be recorded, along with tests for normality and homoscedasticity. The primary statistical objective is to assess whether the changes, pre- vs. post-intervention, in internal imaging metrics of lymphatic clearance or PSFS score are different for the standard CDT therapy or CDT therapy with negative pressure. First, a Student's t-test or Wilcoxon signed-rank test (depending on normality results) will be applied to test the difference between each measurement for the same subject for each of the two therapy sessions. We will also test the difference of any potential carryover effect and we will apply a general linear model approach, in which we include the treatment and treatment-period interaction in the model. Power calculations are based on our preliminary data that observed an improvement in PSFS in five patients on CDT with negative pressure vs. CDT alone, as well as an ability to detect a mean change in T_2 and lymphangiography score pre- vs. post-MLD of N. With the premise that CDT with negative pressure will be at least as good as CDT without negative pressure, with the proposed sample size, we will have 80% power to detect a 40% reduction rate with one-sided type I error = 5%.

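### The Aim 3 linear model includes the treatment-period interaction with no coding and no primary analysis stated, so its treatment estimate can become a low-power first-course contrast; the carryover test is itself too weak to interpret

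*Combined protocol and SAP*

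**What the plan says.** Section 8.0 (Statistical analysis plan) takes as its outcome the "changes, pre- vs. post-intervention, in internal imaging metrics of lymphatic clearance or PSFS score". The first analysis listed is a paired t-test or signed-rank test, "applied to test the difference between each measurement for the same subject for each of the two therapy sessions". The plan then adds "We will also test the difference of any potential carryover effect" and a general linear model, "in which we include the treatment and treatment-period interaction in the model". It does not name a period main effect, a woman or sequence term, or the coding of the factors. It does not say which of these analyses is primary, at what level carryover is tested, or what follows from the result. On power it says "we will have 80% power to detect a 40% reduction rate" at a one-sided 5% level.

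Three other places bear on carryover. Section 1.0, significance item 3, cites pre-clinical evidence of lymphangiogenesis and hopes "to underscore the need for expanding healthcare coverage of these disease-modifying therapies". Section 5.0, item 5, says "There will be a 4-8 week washout period between Visit 11 and Visit 12", whereas the compensation list in item 9 of the same section gives the washout in months. Item 5 also prints the same treatment order for Group 1 and Group 2.

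**The concern.** A cross-over earns its precision by comparing the two treatments within the same woman. The treatment-period interaction in a two-order, two-course design is a comparison between women. If it sits in the treatment model, then under a common software default the coefficient labelled treatment no longer uses each woman as her own control. One sentence of the plan therefore permits several different treatment estimates, with different standard errors.

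The interaction is also the carryover test. A test with little power cannot show that carryover is absent, yet the plan gives no other use for it. Carryover deserves an answer here, because the protocol's own rationale is that the therapies may change the disease.

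**Working it through.** **Inputs.** Power 80% and one-sided 5% come from Section 8.0. The number of women, the SD and the correlation (ρ) between a woman's two course changes are not in the documents. I assume equal numbers, n, in each of two different orders, and show ρ from -0.3 to 0.7. Negative values are included because each change is measured from its own course's baseline (Visits 1 and 12).

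**1. The plan's own figure.** The 80% cannot be reproduced. If the 40% is read as a difference of 0.4 times the mean change under standard CDT, a paired t-test needs about 12 women when the SD of the within-woman difference is 0.5 times that mean, and about 156 when it is 2 times. I therefore take the 80% as given for the within-woman analysis. The noncentrality is 1.645 + 0.842 = 2.4865, and n cancels below.

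**2. What the interaction is.** Let A be CDT alone, B be CDT with negative pressure, and 1 and 2 the courses. One order supplies A1 and B2, the other B1 and A2.
- Interaction: (B1 − A1) − (B2 − A2) = (B1 + A2) − (A1 + B2). This is the difference between orders in the women's totals, so it is aliased with sequence and differential carryover.
- Within-woman treatment effect: ½[(B2 − A1) + (B1 − A2)] = ½[(B1 − A1) + (B2 − A2)], the average over both courses.
- Reference coding, first course as reference: the treatment coefficient is B1 − A1 alone.

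**3. Check on one simulated two-order data set** (30 women, ρ 0.5, mixed models):

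| Model | Treatment estimate (SE) |
|---|---|
| Treatment + period | 1.363 (0.179) |
| Treatment + treatment:period, first course as reference | 1.468 (0.461) |
| Same, second course as reference | 1.259 (0.461) |
| Treatment and a literal 0/1 product column, no period effect | 1.187 (0.243) |
| With interaction, sum-to-zero coding | 1.363 (0.179) |

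The mean of 1.468 and 1.259 is 1.3635, which is the within-woman estimate, as step 2 requires. With fixed woman effects the interaction cannot be estimated (design rank 32 for 33 columns). These are single-sample standard errors. Over 200 simulated trials (24 women, ρ 0.5) the reference-coded coefficient had 4.3 times the variance, and power was 38% against 81%.

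**4. Power of the first-course contrast.** SE(within-woman) = σ√((1−ρ)/n) and SE(first course) = σ√(2/n), so the variance ratio is 2/(1−ρ). Power = Φ(2.4865·√((1−ρ)/2) − 1.645). At ρ = 0.5: Φ(1.243 − 1.645) = Φ(−0.402) = 34%.

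**5. Power of the carryover test.** SE = 2σ√((1+ρ)/n). For a differential carryover equal to the treatment effect, the expected z is 2.4865·√((1−ρ)/(1+ρ))/2. At ρ = 0.5 this is 0.718. Two-sided 5% power is Φ(0.718 − 1.960) + Φ(−0.718 − 1.960) = 11%.

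| ρ (assumed) | Variance ratio | First-course power | Carryover test power, two-sided 5% |
|---|---|---|---|
| −0.3 | 1.5 | 64% | 40% |
| 0 | 2.0 | 55% | 24% |
| 0.3 | 2.9 | 43% | 15% |
| 0.5 | 4.0 | 34% | 11% |
| 0.7 | 6.7 | 25% | 8% |

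At two-sided 10% the carryover test reaches about 52%, 35%, 24%, 19% and 15%. A differential carryover λ biases the within-woman estimate by −λ/2. One as large as the effect halves the estimate if it has the same sign, and inflates it by half if the sign is opposite.

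**6. The order as printed.** If both groups receive the treatments in the same order, treatment and period are the same column (rank 2 of 4 for intercept, treatment, period and interaction). Then neither the interaction nor a first-course contrast exists.

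**The case against.** The strongest reply is that the within-woman comparison is already planned. The paired test comes first, contains no interaction, and the linear model is never called primary. That stands. A reader might infer that the plan gives up the cross-over's precision, but the documents do not support this: the paired test remains, and even in the linear model the shift depends on a coding that the plan does not state. The power loss in step 4 belongs to one reading of the model.

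A reader might also infer a two-stage procedure in which the carryover test selects the analysis, or in which a non-significant result will be declared absence of carryover. Section 8.0 contains neither rule.

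The size of carryover is likewise open. Both treatments include CDT, only differential carryover biases the comparison, and the lymphangiogenesis remark is pre-clinical and not specific to one treatment. A carryover as large as the whole effect is a yardstick, not a prediction.

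Finally, change scores may be weakly or negatively correlated. At ρ = −0.3 the loss is smaller, but first-course power is still 64% and carryover power 40%.

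**Conclusion.** The point holds in a limited form. The model as worded can yield a within-woman estimate, a first-course contrast between women, or something that is neither, depending on coding, and the plan does not say which analysis carries the conclusion. If the first-course reading is taken, the planned 80% falls to between 64% and 25% over the correlations shown. The carryover test detects a full-size differential carryover in 40% down to 8% of trials at two-sided 5%, so a non-significant result would be uninformative.

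These figures rest on the 80% being right for the within-woman analysis, on two different orders with equal numbers, and on assumed correlations. If the order printed in Section 5.0, item 5, is literal, the figures do not apply and treatment is wholly confounded with period.

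**What to change.** In Section 8.0:
- Estimate the treatment effect from a model with treatment, period and woman, without the treatment-period interaction. Name this model, or a period-adjusted paired analysis, as primary.
- Do not put a sequence term in the interaction's place as if it were neutral. In a two-order design it carries the same between-women contrast and the same test, and with fixed woman effects it cannot be estimated.
- State that the carryover result does not decide which analysis is reported.
- Report carryover separately as an estimate with a confidence interval, for example Visit 12 minus Visit 1 compared between orders.
- Always report the first-course comparison (Visit 11 adjusted for Visit 1) as a sensitivity analysis.

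In Section 5.0, reconcile the treatment orders of Groups 1 and 2, and reconcile the washout, printed as 4-8 weeks in item 5 and 4-8 months in item 9.

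The cost is wording and one extra table. All the visits needed are already scheduled. The downside is that carryover is assessed outside the treatment model.

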Aim (2). To identify sub-clinical biomarkers of lymphatic insufficiency using quantitative evaluation of lymphatic vessel anatomy, axillary edema, and interstitial adiposity.

Hypothesis (2). Sub-acute internal imaging markers reflective of tissue microenvironment and interstitial adipose accumulation provide superior discriminatory abilities for portending BCRL progression compared with established risk factors such as BMI, age, and quantity of LNs removed.

Aim (3). To evaluate the impact of CDT with and without graded negative pressure therapy on internal measures of lymphatic dysfunction and edema in patients with chronic BCRL.

Hypothesis (3). Mobilization of protein-enriched hardened tissue using graded negative pressure therapy in conjunction with CDT will reduce (i) superficial markers of interstitial protein accumulation and (ii) lymph stasis, and improve (iii) patient-valued functional outcomes compared to standard CDT and/or exercise and self management treatment strategies.

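### Section 8.0 supports imaging power with a pre- to post-MLD change, but the primary comparison is between two CDT courses that both include MLD, so 80% power for imaging is unsupported

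*Combined protocol and SAP*

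**What the plan says.** The primary objective (section 8.0) asks whether pre-to-post changes in imaging metrics of lymphatic clearance, or in PSFS, "are different for the standard CDT therapy or CDT therapy with negative pressure". The test is a t-test or signed-rank test of the two courses within the same subject.

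The same section gives two preliminary sources for power. One is for PSFS: "Power calculations are based on our preliminary data that observed an improvement in PSFS in five patients" who had CDT with negative pressure versus CDT alone. The other is for imaging: "an ability to detect a mean change in T_2 and lymphangiography score pre- vs. post-MLD". The power statement opens "With the premise that CDT with negative pressure will be at least as good as CDT without negative pressure" and concludes that "we will have 80% power to detect a 40% reduction rate with one-sided type I error = 5" (per cent).

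On treatment content, section 5.0 (item 5) says of Aim 3 subjects that "the MLD screening form will be completed on Visit 1 in preparation for this component of their CDT", and that "they will receive their assigned therapy intervention (CDT alone or CDT with graded negative pressure) at Visits 2-10 and 13-21". Aim 3 in section 2.0 is "To evaluate the impact of CDT with and without graded negative pressure therapy on internal measures of lymphatic dysfunction and edema".

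**The concern.** The imaging basis and the primary test concern different quantities. The first is a change under one condition, before and after MLD. The second is a difference between two treatments, each of which contains MLD. Being able to see the first does not show that the second can be seen.

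Imaging is central to Aim 3. If the 80% is read as covering T_2 and lymphangiography score, a null imaging result would be taken as adequately powered evidence that negative pressure adds nothing. The stated basis does not support that reading.

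**Working it through.** **The plan's own figure.** The 80% cannot be reproduced. Section 8.0 refers to the proposed sample size without giving it, states no effect or SD, and attaches the 40% to no endpoint or scale. The clause on the MLD data ends in a bare letter N. A number may have been lost in the PDF conversion, so nothing is built on that.

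**What the contrast contains.** Assume additive effects. Let M be the MLD effect, C the effect of the other CDT components and G the increment from negative pressure.

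- Change over CDT alone: M + C
- Change over CDT with negative pressure: M + C + G
- Difference d between the courses: (M + C + G) − (M + C) = G

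M cancels if MLD is delivered alike in both courses. If it is not, part of M remains, but the full pre/post-MLD change is still not d. This algebra leaves out period, order and carryover effects, which are taken up under the objection.

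**How much this could matter (illustration).** None of these inputs is in the documents:

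- D and s: mean and SD of the pre/post change, with the same SD in each course
- f: G as a share of D
- rho: within-person correlation between the two courses' changes

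Take a design with exactly 80% power for D at one-sided 5%. Its large-sample noncentrality is 1.645 + 0.842 = 2.487. The between-course difference has mean f × D and SD s × √(2(1 − rho)), so its noncentrality is 2.487 × f / √(2(1 − rho)), and power ≈ Φ(noncentrality − 1.645).

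For f = 0.5:

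- rho = 0: 2.487 × 0.5 / 1.414 = 0.879; power 22%
- rho = 0.5: 2.487 × 0.5 / 1.000 = 1.243; power 34%
- rho = 0.75: 2.487 × 0.5 / 0.707 = 1.758; power 55%
- rho = 0.9: 2.487 × 0.5 / 0.447 = 2.78; power 87%

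| f | rho = 0 | rho = 0.5 | rho = 0.75 | rho = 0.9 |
|---|---|---|---|---|
| 1 | 55% | 80% | 97% | >99% |
| 0.5 | 22% | 34% | 55% | 87% |
| 0.4 | 17% | 26% | 41% | 72% |

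Exact noncentral t results for 12, 20, 27 and 40 completers agree to about 0.001.

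Power for d falls below 80% when f < √(2(1 − rho)), that is, below 1.41, 1.00, 0.71 or 0.45 at the four correlations. Above those values it exceeds 80%. The mismatch can therefore go either way.

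**What can be stated without pilot data.** The detectable d at 80% power is the noncentrality that gives 80% power, divided by √n (paired t-test, one-sided 5%, noncentral t):

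| Completers | Noncentrality | Detectable d (SD of d) |
|---|---|---|
| 12 | 2.655 | 0.77 |
| 20 | 2.580 | 0.58 |
| 27 | 2.554 | 0.49 |
| 40 | 2.531 | 0.40 |

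**The case against.** Five points can be made for the plan.

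1. *The MLD data may only show that the imaging can register a change.* The wording allows this, and the data could also inform the SD of change, which does not cancel. But section 8.0 offers them as a basis for power and gives no such SD. On this reading too, imaging has no stated between-treatment effect. A reader might infer that the trial was sized on an MLD effect; the text does not establish that.

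2. *The power sentence itself concerns CDT with versus without negative pressure.* True, and so does the PSFS pilot. The mismatch is confined to imaging. It does not follow that the 80% belongs to PSFS. The 40% is tied to no endpoint, and a reduction suits the imaging or stasis markers at least as well, since Hypothesis 3 speaks of reducing those and improving function.

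3. *MLD may differ between courses.* Section 1.0 describes CDT with refinements to its individual components, so negative pressure might alter or partly replace MLD within the 75-minute visit. The documents do not say. This stands as a limit on the cancellation, not as support for using the whole MLD change.

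4. *d may not isolate negative pressure.* This stands. Section 5.0 (item 5) gives Groups 1 and 2 the same order, CDT alone first. As written, d is the increment plus any period, order or carryover effect.

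5. *The power figures rest on assumptions.* They do. They also take the SD of a pre/post-MLD change to equal that of a nine-visit course. At rho = 0.9, half the MLD effect is enough to keep power above 80%.

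**Conclusion.** The point holds for imaging. The stated imaging basis belongs to a different contrast from the primary one, and the documents give neither a between-treatment imaging effect nor an SD of the within-person difference. The 80% is therefore unsupported for T_2 and lymphangiography score.

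A reader might go further and infer that the imaging comparison is underpowered, or that the 80% is wrong. The documents do not support that: with N, effect and SD unstated, actual power cannot be computed. The range of 22% to 87% at f = 0.5 shows how little a pre/post-MLD effect says about power for this comparison. It is not an estimate for this trial. It rests on additive effects, MLD delivered alike in both courses, equal SDs of change, and assumed f and rho.

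This should be fixed: the correction is cheap, and it changes what a null imaging result can be taken to mean.

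**What to change.** In section 8.0, replace the power statement with text along these lines:

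> Power refers to d, the within-person difference between the pre-to-post change over the course with negative pressure and that over the CDT-alone course. The 80% applies to [endpoint, with the scale and meaning of the 40%, the assumed SD of d, and N]. Pre- to post-MLD imaging data are background on measurement sensitivity and are not an effect size for this comparison. For T_2 and lymphangiography score, the difference detectable with 80% power (paired t-test, one-sided 5%) at N completers is [x] SD of d. Imaging results are reported as mean d with a 90% confidence interval; non-significance is not read as absence of effect.

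For x, use 0.77 with 12 completers, 0.58 with 20, 0.49 with 27 or 0.40 with 40, or recompute at the actual N. If the sponsor holds a between-treatment imaging estimate, state it with its SD and give power on that instead. The sponsor must name the endpoint for the 80%; PSFS should not be entered unless the sponsor confirms it.

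Separately, reconcile the identical treatment order for Groups 1 and 2 in section 5.0 (item 5) with the cross-over design of Aim 3 before d is read as the negative-pressure effect.

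The power change is SAP wording and needs no new data. Its cost is that, unless a between-treatment imaging estimate exists, the plan gives up any claim of 80% power for imaging.
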